#### **11.2.2.2 Missing Data**

For efficacy variables, with repeated measures, a mixed model will be employed with no additional imputation for missing values, i.e., based on “observed cases”, except where otherwise specified.

Follow-up and continued collection of efficacy data for patients who discontinue treatment will be made. These data will be included in the sensitivity analysis for primary endpoints estimating a treatment effect taking loss of effect after discontinuation into account. Because complete follow-up of all patients discontinuing treatment may not be possible, a method to replace missing data for patients who discontinue the study will be prespecified (in the SAP) taking into account loss of effect after discontinuation (for example multiple imputation).

No other replacement of missing values will be planned.

#### **11.2.2.3 Demographic and Baseline Characteristics**

Descriptive summaries of demographics and other baseline characteristics (including medical and surgical history) will be presented by treatment group and overall using the FAS.

Prior medication will be summarized by treatment group and overall using the safety analysis set.

#### 11.2.2.4 Subject Disposition

The following will be summarized (by treatment group and overall where applicable):

- Patients enrolled (who signed the informed consent)
- Patients randomized
- Patients treated
- Patients completing the study/withdrawing early (including withdrawal reason)

Additionally, patients enrolled, included in the safety, in the FAS, and in the PP analysis set will be summarized by region.

#### 11.2.2.5 Evaluation of Primary Efficacy Variables

The responder endpoint based on change in fasting bile acids will be analyzed in terms of the proportion of patients achieving the event of interest. Patients in need of rescue therapy, i.e., biliary diversion will be classified as non-responders after the biliary diversion.

Generalized linear mixed modelling (GLMM) will be used with a logistic link, to allow for repeated assessments over time. The model will include baseline value, treatment group, PFIC class, age class, region, visit, and visit\*treatment group interaction. The treatment by visit interaction will remain in the model regardless of significance. Region will be included in the model as a random effect. The contrasts of primary interest will be the treatment difference at Week 24; also, the difference at Week 4, Week 8, Week 12, and Week 18 will be estimated and analyzed. An unstructured covariance matrix will be used to model the within-subject error. Another covariance structure may be chosen if the fit of this structure fails to converge. Model diagnostics checks will be made to ensure appropriate fit.

The primary analysis of the change from baseline in pruritus score (indexed by observer-reported scratching) will be analyzed using a mixed model repeated measures (MMRM) analysis. The contrast of primary interest will be treatment difference at Week 24 but also the differences at Week 4, Week 8, Week 12, and Week 18 will be estimated and analyzed. Baseline pruritus score will be included as covariate. The model will include baseline value, treatment group, PFIC class, age class, region, visit, and visit\*treatment group interaction. The treatment by visit interaction will remain in the model regardless of significance. Region will be included in the model as a random effect and will be defined on country level. An unstructured covariance matrix will be used to model the within-subject error. Another covariance structure may be chosen if the fit of this structure fails to converge.

Non-parametric approach may be considered if more appropriate.

The primary analyses will be based on the FAS.

To assess the robustness of the primary efficacy analysis, the following analyses will be performed:

- Primary efficacy analysis using the PP set
- Analyses to investigate the influence of missing values, for example, by using pattern mixture models and tipping point analysis

Subgroup analyses will also be performed for each of the 3 age groups (6 months to 5 years, 6 to 12 years, and 13 to  $\leq 18$  years) and for patients who were not included in the previous Study A4250-003.

Several sensitivity analyses will be performed, such as the following:

- Cochran Mantel Haenzsel test stratified on PFIC class to compare the proportion in fasting bile acid responder endpoint at the end of treatment in the two A4250 dose groups to placebo group. Dropouts will be treated as non-responders
- Based on the primary analysis including the interaction age class\*treatment
- Same as primary analysis in which the random factor region is considered as fixed factor. The region\*treatment interaction will also be explored
- Same as primary analysis including the interaction PFIC\*treatment

Other sensitivity analyses may be performed and will be detailed in the SAP.

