## 7 INVESTIGATIONAL PLAN

### 7.1 Overall Study Design and Plan

#### 7.1.1 Description

This is a double-blind, randomized, placebo-controlled, Phase 3 study to investigate the efficacy and safety of 40 µg/kg/day and 120 µg/kg/day of A4250 compared to placebo in children with PFIC (deficiencies of FIC1 or BSEP).

Study data will be periodically reviewed by an unblinded Data Safety and Monitoring Board (DSMB).

The study includes a 35- to 56-day Screening Period followed by a 24-week Treatment Period and a 4-week Follow-Up Period.

After completion of the Screening Period, eligible patients (20 per treatment group) will be randomized on Day 0 (Visit 3) in a 1:1:1 fashion to receive 40 µg/kg/day or 120 µg/kg/day of A4250, or a matching placebo.

Patients who complete the Treatment Period and Visit 9 (Day 168) in this study will be invited to participate in a 72-week open-label extension study (A4250-008, EudraCT Number 017-002325-38, subject to a separate study approval) in which all patients will receive active treatment. A patient who prematurely withdraws due to no improvement/intolerable symptoms, and has completed at least 12 weeks of the Treatment Period and End of Treatment (EOT) Visit, will also be offered the opportunity to enter Study A4250-008.

Visit windows applicable to each visit are presented in the schedule of assessments ([Table 1](#)). There will be up to 10 clinic visits during the study ([Figure 1](#)) and one scheduled telephone contact, as follows:

- Visit 1: Screening Period start. Patient is considered enrolled after signing the informed consent form (ICF) (Days -56 to -35)
- Visit 2: second Screening Visit (Days -28 to -7)
- Visit 3: Randomization Visit (Day 0)
- Telephone Contact 1: (Day 14)
- Visit 4: Clinic Visit (Day 28)
- Visit 5: Clinic Visit (Day 56)
- Visit 6: Clinic Visit (Day 84)
- Visit 7: Clinic Visit (Day 126)
- Visit 8: Clinic Visit (Day 154)
- Visit 9: Clinic Visit, EOT (Day 168)

- Visit 10: Follow-Up Visit, 28 days after last dose of study drug (Day 196). All patients continuing in Study A4250-008 will not have this Follow-up Visit.

Additional clinic visits may be required for patients who need direct site assistance, e.g., due to AE monitoring, to fulfil screening requirements, and/or for safety maintenance.

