### 7.1.3 Study Procedures and Assessments

#### 7.1.3.1 Screening Period (Days -56 to 0)

##### Day -56 to Day -35/Clinic Visit 1

Patients will undergo a Screening Visit up to 56 days prior to the planned first day of study treatment. Screening procedures and assessments are as follows:

- Obtain written informed consent
- Assess inclusion/exclusion criteria ([Section 7.2](#))
- Record demographics (age, full date of birth, gender, race, and ethnicity)
- Document concomitant medications
- Medical and surgical history (date of diagnosis of PFIC Types 1 or 2, prior investigational medications for PFIC, historical liver function test [LFT] values, any surgery performed, any other diagnosis, and historical liver biopsy data)
- Blood sample for genetic testing
- Collect, if available, past confirmatory clinical genetic laboratory report for PFIC1/PFIC2 and send to central reader for review
- Physical examination, including voluntary photography ([Section 10.2.5](#))
- Skin examination ([Section 10.2.5](#))
- Vital signs ([Section 10.2.6](#))
- eDiary training and compliance requirements; patients begin daily recording of pruritus using the eDiary ([Appendix 2](#))
- Clinical chemistry ([Section 10.2.1](#))
- s-BA ([Section 9.2.1](#))
- Serum pregnancy test for girls of who have reached menarche
- AE monitoring

##### Day -28 to Day -7/Clinic Visit 2

A second Screening Visit will be performed. Screening procedures and assessments are as follows:

- Review concomitant medications
- Vital signs ([Section 10.2.6](#))
- Albireo PRO/ObsRO eDiary review for itching, scratching, and sleep scores and compliance
- Urinalysis ([Section 10.2.1](#))

- s-BA ([Section 9.2.1](#))
- International normalized ratio (INR)
- Fat-soluble vitamins A and E
- Urine pregnancy test for girls of who have reached menarche
- AE monitoring

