## 7.2 Study Population

A total of 60 patients with clinical diagnosis of PFIC Type 1 or 2 that have been genetically confirmed will be randomized.

An attempt will be made to randomize a minimum of 10 patients from each age category (6 months to 5 years, 6 to 12 years, and 13 to  $\leq 18$  years).

A maximum of 5 patients that were treated in Study A4250-003 will be allowed to participate in this study.

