12. Serum ALT  $>10 \times$  upper limit of normal (ULN) at Screening
13. Serum ALT  $>15 \times$  ULN at any time point during the last 6 months unless an alternate etiology was confirmed for the elevation
14. Total bilirubin  $>5 \times$  ULN at Screening
15. Patient suffers from uncontrolled, recalcitrant pruritic condition other than PFIC. Examples include, but not limited to, refractory atopic dermatitis or other primary pruritic skin diseases
16. Any patient who is pregnant or lactating or who is planning to become pregnant within 24 weeks of randomization
17. Sexually active males and females who are not using a reliable contraceptive method with  $\leq 1\%$  failure rate (such as barrier protection, hormonal contraception, intrauterine device, or complete abstinence) throughout the duration of the study (from signed informed consent through Follow-up, Visit 10).
18. Patient with a past medical history of alcohol or substance abuse will be excluded. Patient must agree to refrain from illicit drug and alcohol use during the study
19. Administration of bile acid or lipid binding resins and medications that slow GI motility (Refer to [Appendix 1](#) – Concomitant Medications Prohibited during the study)
20. Patient has had investigational exposure to a drug, biologic agent, or medical device within 30 days prior to Screening, or 5 half-lives of the study agent, whichever is longer
21. Patient who has been previously treated with an IBAT inhibitor whose pruritus has not responded to treatment
22. Any other conditions or abnormalities which, in the opinion of the investigator or Medical Monitor, may compromise the safety of the patient, or interfere with the patient participating in or completing the study

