#### 8.3.3 Blinding and Randomization of Study Drug

A double-blind design is employed so that both the investigators and the patients will be unaware of the treatment assignment during the study.

After written informed consent is obtained from an eligible patient, an 8-digit patient identification number will be assigned. The first 2 digits will denote the country, followed by a 3-digit site number and a 3-digit patient sequence number. This number will be created and allocated by the Interactive Web Response System (IWRS), when the patient first enters the system at Screening. The randomization codes will be computer-generated by XXXXXXXXXX

██████████, and kept by a statistician independent from the project team. The randomization will be done in blocks and stratified according to PFIC class (Type 1 and 2) and age class (6 months to 5 years, 6 to 12 years, and 13 to ≤18 years) to ensure approximate balance between dose schemes (1:1:1). A separate randomization list will be prepared for the maximum 5 patients from Study A4250-003 regardless of stratification. Randomization codes will be assigned sequentially as patients become eligible for randomization.

Patients who are eligible for randomization will be assigned a unique 4-digit randomization number by IWRS. This randomization number identifies which treatment will be allocated to the patient. Patients who withdraw from the study after randomization visit are not to be replaced and their randomization number will not be reused.

To ensure blinding, the study drug and the matching placebo have the same shape and size. Patients will receive capsule(s) of A4250 according to their dose group or capsule(s) of matching placebo once a day during the double-blind Treatment Period. Labels on the study drug containers will not identify the treatment that a patient is randomized to. Traceability of the treatment is ensured by the study drug number.

The 5-digit study drug number will identify study drug packs and will be detailed on the study drug label. Dispensing of study drug will be coordinated by IWRS.

The system will assign a study drug number corresponding to the randomization arm. The randomization number will be used in the background only to ensure no unblinding and will not be displayed to end-users in the IWRS.

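### The subgroup without Study A4250-003 patients can still contain children selected for response to another IBAT inhibitor

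*Protocol*

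**What the plan says.** Criterion 21 in Section 7.2.2 reads: "Patient who has been previously treated with an IBAT inhibitor whose pruritus has not responded to treatment". It names the drug class, with no reference to a product or a study. Criterion 20 bars investigational exposure only when it falls "within 30 days prior to Screening, or 5 half-lives of the study agent, whichever is longer"; older exposure is allowed.

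The other provisions on prior exposure concern one study. Section 7.2 states: "A maximum of 5 patients that were treated in Study A4250-003 will be allowed to participate in this study". Section 8.3.3 gives those patients their own list: "A separate randomization list will be prepared for the maximum 5 patients from Study A4250-003 regardless of stratification". Section 11.2.2.5 plans subgroup analyses for the three age groups "and for patients who were not included in the previous Study A4250-003".

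The primary models have no term for earlier IBAT treatment: "The model will include baseline value, treatment group, PFIC class, age class, region, visit, and visit\*treatment group interaction". The Visit 1 medical history in Section 7.1.3.1 does collect "prior investigational medications for PFIC", and Section 10.2.3 repeats this.

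**The concern.** Criterion 21 works in one direction. Among children who have already had an IBAT inhibitor, it removes those whose pruritus did not improve and keeps those whose pruritus did. The children who remain have been selected for response to the class, and on the symptom that is the US primary endpoint and the main secondary endpoint for the EU and the rest of the world. That endpoint is scored by caregivers, who may have watched the child improve on a similar drug.

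A reader of the results will want to know whether the effect holds without these children. The analysis nearest to that question leaves out one source of them, Study A4250-003, and keeps any other.

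**Working it through.** No stated figure is in dispute. For the record, the two powers in Section 11.1 reproduce: 84.6% by Fisher's exact test (stated 84%) and 83.6% by the noncentral t with 38 degrees of freedom (stated 83%), each with 20 per group at a one-sided 1.25%. The check is a reading of the provisions against each possible treatment history. Section 5.1 makes A4250 itself an IBAT inhibitor. Criterion 20 is assumed to be met throughout.

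| Treatment history | Eligible under criterion 21? | Under the cap and separate list? | In the Section 11.2.2.5 subgroup? |
|---|---|---|---|
| No IBAT inhibitor | Yes | No | Yes |
| Study A4250-003, pruritus responded | Yes, at most 5 | Yes | No |
| Study A4250-003, pruritus did not respond | No | n/a | n/a |
| Another IBAT inhibitor, pruritus responded | Yes, no limit | No | **Yes** |
| Another IBAT inhibitor, pruritus did not respond | No | n/a | n/a |

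The fourth row is the gap. Nothing else in the protocol closes it: no stratification factor, model term or listed sensitivity analysis refers to earlier IBAT treatment.

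**What the cap bounds.** Section 11.1 aims for 60 to 70 patients. Study A4250-003 patients can make up at most 5/60 = 8.3% or 5/70 = 7.1% of them, so the subgroup keeps at least 60 − 5 = 55 or 70 − 5 = 65. The fourth row has no corresponding bound, and the protocol gives neither a count nor a response size for it.

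**Scale only.** The pruritus endpoint is a mean change. If *k* such children fall in an active arm of 20, and each improves by *e* points more than an otherwise similar untreated child would, the raw arm mean moves by *k* × *e* / 20. The value of *e* is an assumption. Setting it at 1.0, the size of the treatment difference assumed in Section 11.1, gives:

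- *k* = 0: shift 0
- *k* = 1: 1 × 1.0 / 20 = 0.05 points
- *k* = 2: 2 × 1.0 / 20 = 0.10 points

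This shows the weight of one child in an arm of this size. It is not an estimate of what will happen.

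**The case against.** **Purpose.** Section 11.2.2.5 gives no reason for the subgroup and lists it beside the age groups, apart from the robustness analyses (the per protocol set and the missing-data analyses). A reader might infer that it was intended as an IBAT-naive population and fails its own aim. The protocol does not say so. In the superseded version of 20 September 2017 the same patients formed a modified full analysis set used for robustness, but that version had no criterion on earlier IBAT treatment. The restriction then dealt with participation in an earlier study of this drug. This objection stands: the subgroup does what it says, and the point is that it now answers a narrower question than criterion 21 raises.

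**Target population.** A reader might also infer that the objective concerns untreated children. Section 6.1 says children with PFIC Types 1 and 2, so previously treated children belong to the target.

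**Validity.** Allocation is 1:1:1 and experienced children can fall in any arm, so a claim of inflated Type I error would be wrong.

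**Numbers.** No passage identifies a child with PFIC treated with an IBAT inhibitor outside Study A4250-003. Section 5.2.1 says no drug is approved and lists no IBAT inhibitor among the off-label options. Section 5.2.2 describes the other A4250 studies as being in healthy volunteers and in primary biliary cholangitis. The count may be zero. Criterion 21 also selects on pruritus, so any effect on the bile acid responder rate is indirect, and the documents support no figure for it.

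**Left to the SAP.** Further sensitivity analyses are deferred to the SAP, and an additional subgroup could be defined there. But the protocol itself fixes this subgroup and its definition, so that definition is open to comment.

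**Cap and list.** It is tempting to extend both to every IBAT-experienced child. The list operates without stratification, so more children would lose balance on PFIC type and age in a trial of about 60, and a wider cap would cost recruitment in a rare disease. The documents do not support that step.

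**Conclusion.** The point holds as a mismatch between two definitions. Eligibility selects on response to the class, while the subgroup excludes on participation in one study. Responders to another IBAT inhibitor can therefore remain in the subgroup, and it cannot show whether the effect depends on children selected in this way. Pruritus is the endpoint most exposed.

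The size is unknown. It depends on how many such children enrol, which may be few or none, and on how much more they respond than untreated children. Significance testing is unaffected; what is at stake is the size of the effect and the patients to whom it applies. This is a modest improvement.

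**What to change.** In Section 11.2.2.5, replace the restriction to patients outside Study A4250-003 with: patients with no previous exposure to any IBAT inhibitor, including A4250 in Study A4250-003. Add that the number of IBAT-experienced patients will be reported by arm.

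The new definition still leaves out every Study A4250-003 patient. If no other experienced child enrols, the two definitions give the same subgroup, and the count by arm will show that.

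The source is the Visit 1 history of investigational PFIC medication. The medication record in Section 8.7 would not serve, because it reaches back only 1 month before Visit 1 for stopped drugs. Sites must in any case establish earlier IBAT treatment to apply criterion 21. It is worth confirming that the eCRF entry allows the drug class to be identified.

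The cost is a change of wording. Eligibility, the cap of 5, the separate list and the primary analysis are unchanged.

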#### **11.2.2.6 Evaluation of Secondary and Exploratory Efficacy Variables**

The change in the secondary and explorative endpoints such as s-BA, total bilirubin, ALT, growth and patient-reported itch severity will also be analyzed using the MMRM model as specified for the primary analysis. Nonparametric methods may be applied as an alternative approach for some endpoints, if appropriate. Change in growth (weight for age and BMI for age) will also be displayed using graphical presentations.

Proportions of responders (e.g., meaningful reduction in itch severity and scratching at Week 24) will be analyzed using the GLMM model as specified for the primary analysis.

Comparisons of the change from baseline at Week 24 in PedsQL between the treatment groups will be conducted using analysis of covariance. The model will include terms for baseline, PFIC class, age class, region, and treatment.

Undergoing biliary diversion surgery and/or listed for liver transplant, all-cause mortality, and liver decompensation events will mainly be analyzed by using descriptive statistics. Kaplan-Meier curves will be used when appropriate for time to event data.

Other exploratory variables (Global Symptom Relief, biochemical markers and measures of bile acid synthesis, Albireo PRO and ObsRO sleep parameters, PELD/MELD score, APRI score, and Fib-4 score) will be analyzed descriptively for categorical and continuous data, as applicable. For continuous data, the change from baseline will be analyzed in addition to the actual visit values. For categorical data, shift tables or frequency and percentages of patients will be presented as appropriate.

In addition, subgroup analyses will be performed for each of the 3 age classes (6 months to 5 years, 6 to 12 years, and 13 to  $\leq 18$  years).

#### **11.2.2.7 Evaluation of Safety Variables**

Safety data will be analyzed using descriptive statistics and summaries by treatment group of SAEs, AEs, vital signs, clinical laboratory tests (hematology, clinical chemistry and urinalysis), and concomitant medication. Analyses will be performed using the safety analysis set.

Summaries of AEs (coded according to the Medical Dictionary for Regulatory Activities [MedDRA] system organ class [SOC] and MedDRA preferred term) will include the following:

- Overview of the incidence of TEAEs (TEAEs, drug-related TEAEs, TEAEs leading to study discontinuation, and treatment-emergent SAEs)
- TEAEs by SOC and preferred term
- Intensity of TEAEs by SOC and preferred term
- Drug-related TEAEs by SOC and preferred term
- TEAEs leading to study discontinuation by SOC and preferred term
- Treatment-emergent SAEs by SOC and preferred term

Concomitant medication use during the Treatment Period will be summarized by Anatomical Therapeutic Chemical (ATC) class and World Health Organization (WHO) preferred name.

Summaries of vital signs will be presented. For each visit, the actual results and the change from baseline, and the number and percentage of patients with potentially clinically significant (PCS) values observed post-baseline will be presented.

Summaries of clinical safety laboratory data will be presented. For each visit, the actual result and the change from baseline, and the number and percentage of patients with PCS values observed post-baseline will be presented.

Data listings will be provided for each patient for all safety parameters.

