### 7.2.3 Withdrawal of Patients

Patients/caregivers will be informed that they have the right to withdraw from the study at any time, without prejudice to their medical care, and that they are not obliged to state their reasons.

Any withdrawal, and reasons for withdrawal, must be fully documented in the electronic case report form (eCRF) and source documents and the patient followed by the investigator/investigative staff. Even after the study is completed at the Follow-up Visit, the investigator/investigative staff will, regardless of reason for withdrawal, record any patient data they receive concerning SAEs, and all drug-related non-serious AEs, and subsequently report these to Albireo. Withdrawn patients will not be replaced.

Patients will be withdrawn in the following circumstances:

- A patient's/caregiver's desire for withdrawal for any reason
- Lost to follow-up (every effort must be made to contact the patient/caregiver; a certified letter must be sent)
- An AE that, in the opinion of the investigator, necessitates withdrawal
- A worsening of the symptoms related to diarrhea occurs
- Death
- Patient/caregiver estimation of lack of improvement/intolerable symptoms
- A patient's/caregiver's substantial noncompliance (eDiary and study drug compliance) or protocol violation
- An investigator's opinion that continuing the patient in the study is not appropriate. The investigator may withdraw a patient at any time, if it is considered to be in the patient's best interest

A patient who prematurely withdraws due to no improvement/intolerable symptoms, and has completed at least 12 weeks treatment in the double-blind study, will be offered the opportunity to enter open-label Study A4250-008. A patient who withdraws from treatment prematurely and will not enter Study A4250-008 will be requested to complete all visits and safety assessments per the current protocol (A4250-005). As a minimum, patients will have EOT (Visit 9) assessments at the time of withdrawal and a follow-up assessment (Visit 10) 28 days following the last dose of study drug, and the patient will be recorded as withdrawn.

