## 10 ASSESSMENT OF SAFETY

The timing and frequency of safety assessments are described in [Section 7.1.3](#) and in [Table 1](#) above.

The primary safety analysis for this study will include the incidence of total treatment-emergent adverse events (TEAE) and TEAEs categorized by causality, severity, and seriousness assessments made by the investigator by comparing study drug exposure to placebo.

Trends in safety will also be evaluated for the following assessments:

- Physical examinations
- Concomitant medications
- Vital signs
- Laboratory test results (including clinical chemistry, hematology, urinalysis, AFP, and fat-soluble vitamins A, D, and E)
- Abdominal ultrasound
- Discontinuations due to AEs

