#### **11.2.2.8 Compliance and Exposure**

Exposure will be analyzed by calculating the number of days with exposure to study drug. Results will be presented by treatment group using the safety analysis set.

The percentage compliance will be described by treatment group and the number of patients with a compliance  $< 80\%$ , between  $80\%$  and  $120\%$ , and  $> 120\%$  will be presented based on the safety analysis set.

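### TEAEs are compared by crude incidence although patients may leave blinded follow-up from Week 12, so unequal exits between arms would distort the harm comparison, probably modestly and against A4250

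*Protocol*

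**What the plan says.** Section 10 states that "The primary safety analysis for this study will include the incidence of total treatment-emergent adverse events (TEAE"), with TEAEs also "categorized by causality, severity, and seriousness assessments made by the investigator by comparing study drug exposure to placebo". Section 11.2.2.7 carries this out with six adverse event summaries by treatment group, the first being an "Overview of the incidence of TEAEs (TEAEs, drug-related TEAEs, TEAEs leading to study discontinuation, and treatment-emergent SAEs"). The other five break TEAEs down by system organ class and preferred term. None uses time at risk, time to first event or a common cut-off.

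Exposure is handled separately in Section 11.2.2.8: "Exposure will be analyzed by calculating the number of days with exposure to study drug". It is presented by treatment group but linked to no adverse event comparison.

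The design is a screening period "followed by a 24-week Treatment Period and a 4-week Follow-Up Period". Section 7.1.1 adds an early route out: "A patient who prematurely withdraws due to no improvement/intolerable symptoms, and has completed at least 12 weeks of the Treatment Period" and the End of Treatment visit, will also be offered A4250-008, "in which all patients will receive active treatment". Section 7.2.3 repeats the offer. It asks only those early withdrawers who will not enter A4250-008 to complete all remaining visits and safety assessments. Patients who enter A4250-008 have no Visit 10 in this study.

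**The concern.** Crude incidence compares arms fairly only when they are observed for about the same time. Here the planned way of cutting blinded observation short, by up to half of the 24 weeks, is opened by an outcome that the drug is meant to change. If more patients leave one arm, that arm has less time in which to record a first event, and its percentage is too low for that reason alone.

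At stake is the safety comparison behind the tolerability objective in Section 6.2, chiefly for events that accumulate over time. Events that cluster in the first weeks are much less affected, because they have mostly occurred before anyone can take the exit.

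**Working it through.** The protocol gives no safety figure to reproduce and no exit rate by arm, so the size can only be illustrated.

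**Inputs from Section 11.1.** Mean change in scratching score is -0.6 on placebo and -1.6 on A4250, with SD 0.95 and about 20 patients per group. These are the inputs to the stated 83% pruritus power. A two-sample t calculation (38 degrees of freedom, one-sided 1.25%) gives 83.6%, so they are read correctly.

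**Step 1: share with no reduction in scratching.** Assume normally distributed change and take no improvement to mean a change of zero or above.

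- Placebo: 1 - Φ(0.6/0.95) = 1 - Φ(0.632) = 0.264
- A4250: 1 - Φ(1.6/0.95) = 1 - Φ(1.684) = 0.046

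**Step 2: exits.** Assume that a share q of these patients leaves at Week 12. The leaving fraction is f = 0.264q on placebo and 0.046q on A4250. Mean blinded observation is 24 - 12f weeks. At q = 1 this is 20.8 weeks on placebo and 23.4 on A4250.

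**Step 3: crude incidence with equal true harm.** Take 24-week risk I = 30% in both arms and a constant hazard. Risk by Week 12 is 1 - 0.70^0.5 = 16.3%. Crude incidence = (1 - f) × 30% + f × 16.3%.

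| q | Placebo | A4250 | Difference (points) | Ratio |
|---|---|---|---|---|
| 0.25 | 29.1% | 29.8% | 0.7 | 1.03 |
| 0.50 | 28.2% | 29.7% | 1.5 | 1.05 |
| 0.75 | 27.3% | 29.5% | 2.2 | 1.08 |
| 1.00 | 26.4% | 29.4% | 3.0 | 1.11 |

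The true ratio is 1.00 in every row.

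**Step 4: what changes the answer.**

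- *Earlier events.* If 75% of the 24-week hazard falls before Week 12, risk by Week 12 is 1 - 0.70^0.75 = 23.5%. The q = 1 row becomes 28.3% against 29.7%, a difference of 1.4 points.
- *Larger exits.* Set the exit fractions directly, without Step 1, at 50% on placebo and 10% on A4250. The 30% event then shows as 23.2% against 28.6%, a difference of 5.5 points.
- *Exits the other way.* If 10% leave placebo and 25% leave A4250, the figures are 28.6% and 26.6%. The difference is then -2.0 points and the sign reverses.

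**Step 5: random error for comparison.** At 20 per arm and 30% incidence, the standard error of a difference is √(2 × 0.3 × 0.7/20) = 14.5 points.

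**The case against.** The strongest reply is that exposure-adjusted rates are ordinary SAP content, that Section 11.2.2.1 promises a more detailed SAP, and that Section 11.2.2.7 lists what the summaries will include and so sets a minimum. It is true that nothing there forbids an adjusted rate. What remains is that the measure the protocol does choose for its primary safety comparison fits poorly with its own exit rule, and that no time-based measure is paired with it.

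The protocol also partly exposes the problem. Exposure days are shown by group, early withdrawal with reason is tabulated by group (Section 11.2.2.4), and laboratory results are shown visit by visit, so Weeks 4, 8 and 12 can be compared before the exit matters. This makes an imbalance visible but does not correct the adverse event percentages for it.

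The safety analysis is descriptive, and the illustrated bias is small beside a standard error of 14.5 points. That limits the consequence. The standard error measures chance variation, whereas this error is systematic and would affect every accumulating event.

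A reader might go further and infer that leavers will be mostly placebo patients and that A4250 will therefore look falsely worse. The documents do not support that. They give no exit rate by arm, and intolerable symptoms, which can arise on active drug, open the same route. A reader might also size the leaving pool from the 90% and 40% bile acid non-responders implied by Section 11.1. That is the wrong input, because Section 9.2.1 keeps bile acid results blinded during treatment. Section 7.2.3 bases this withdrawal on the patient's or caregiver's own estimate of improvement, so the scratching assumptions are the nearer guide.

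**Conclusion.** The concern stands in conditional form. Crude TEAE incidence is distorted if exits from Week 12 differ between arms. On the protocol's own pruritus assumptions more placebo exits are likelier, so A4250 may look somewhat worse than it is. For a 30% event with constant hazard and exits at Week 12, the distortion is about 1 to 3 percentage points (ratio 1.03 to 1.11).

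This size rests on four things the protocol does not state: normally distributed change scores, no improvement defined as no reduction in scratching, the share of such patients who leave, and when they leave. A stricter patient view of improvement would enlarge the pool. Later exits or earlier events would shrink the effect, and more exits from A4250 would reverse it. The remedy is the same in either direction and is cheap, so the change is worth making, but as an addition to the crude tables and not as a replacement for them.

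**What to change.** In Section 11.2.2.7, keep the crude n (%) tables and add two things.

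1. For TEAEs, drug-related TEAEs and treatment-emergent SAEs, report by treatment group the patients with a first event per patient-time under blinded adverse event observation, censored at the end of that observation. The denominator must match the window in which events are counted. The drug-exposure days of Section 11.2.2.8 are a different quantity, because patients off drug may still be under observation. State where the window ends for patients entering A4250-008: Section 10.1.2 runs collection to Visit 10 or 28 days after the last dose, footnote m of Table 1 runs it to study discontinuation, and the TEAE definition has no end date.
2. One overview table of TEAEs with onset through Day 84, before the open-label exit opens.

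The cost is a wording change and a few extra tables from data already collected. Study conduct and the exit rule are untouched. The rates assume a roughly constant hazard, so events that cluster early should be read from the Day 84 table.
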